### Calculation of Sample Size & Sampling Strategy

We anticipate approximately 5%, perhaps 10%, of study participants will test positive for HIV and not be eligible for the analysis of health facility HIV testing within 6 months among those testing **HIV negative or refusing testing**. We further estimate that 70% will complete the healer-initiated HIV test, 60% will participate in additional counseling sessions, and 50% will attend an open house. Because study participants had no history of HIV testing in the prior year, we anticipate the primary endpoint of uptake of HIV testing at the health facility will be low, approximately 30%. Finally, given the importance of identifying sub-groups which may benefit the most from the intervention components, we have powered our study to detect significant associations within strata of potential modifiers (e.g., gender). We utilized Stata psim command to conduct 500 simulations each for all combinations of the parameters described above to estimate power to detect a range of RRs.

Given our sample size of 600 study participants, with 5% testing HIV+, and for a modifying variable distributed 50%/50%, we have ~90% power to detect stratum-specific RRs of 2.0 for each intervention component (Table 1). We still retain >80% power to detect RRs of 2.25 even if uptake of HIV testing in control group is as low as 20%. Similarly, if the modifying variable is distributed 40%/60%, we retain ≥80% power to detect stratum-specific RRs of 2.0 (Table 2). Thus, the high power due to our sample size allows for robust assessment and identification of intervention associations within key subsets of participants (gender, stigma, etc.).

Given that we only anticipate 10-30 participants to test HIV+, we will be underpowered to detect a meaningful association for how the intervention components associate with uptake of ART services at the health facility within three months among those testing **HIV positive**. However, the proportion testing positive, the proportion linking to ART care, and the magnitude of the RR for the intervention components will provide important preliminary data for whether this intervention improves ART care and retention, and not just linkage to HIV prevention services (such as follow-up HIV testing in those who are negative).

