### **Data Analysis**

Given that participants may complete none, one, two, or all three of these intervention components, we will consider four different intervention component variables to the Healer-Clinician HIV Prevention Collaborative intervention: (1) Uptake of healer-initiated HIV counseling and testing (vs. those who did not), (2) Participation in additional counseling sessions (vs. those

who did not), (3) Attendance at  $\geq 1$  Open House event at the health facility (vs. those who did not), and (4) An index ranging from 0 to 3 indicating the number intervention components completed.

The primary outcome among those testing HIV negative or refusing testing is uptake of health facility HIV testing within 6 months. We will operationalize the outcomes in the positive (e.g., tested at health facility within 6 months) such that the risk ratios (RR) for the intervention components will be  $>1.0$  if effective. We will estimate the association of each intervention component individually (numbers 1-3 above) using separate regression models that are each further stratified by potential modifiers such as gender, age, sexuality, immigration status, and other baseline characteristics. We will use *modified Poisson regression* models for each intervention component to estimate risk ratios and 95% confidence intervals.

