#### **9. Limitations**

This pilot study is not a randomized controlled trial, thus we cannot compare uptake of healer-initiated testing with other modalities; however, we will capture uptake of healer-initiated testing, impact of uptake on key psychological outcomes, including HIV stigma and mistrust in the health system, and obtain data on linkage of participants to the health system - key elements to developing and powering a larger randomized controlled trial. We have framed the intervention and subsequent analysis in the cultural context and are collecting data to specifically identify/inform subgroup effects, including sex. While we may be underpowered to detect some of these effects in small subgroups, a low p-value on heterogeneity tests will provide us with a signal for further investigation in a sufficiently powered future RCT.

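### The plan seeks the sub-groups that benefit most but reports only stratum-specific risk ratios, which do not show absolute gain if baseline uptake differs between strata

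*Combined protocol and SAP*

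**What the plan says.** Under Calculation of Sample Size & Sampling Strategy, the protocol explains why it powers within strata: "given the importance of identifying sub-groups which may benefit the most from the intervention components". Tables 1 and 2 then give power for RRs of 1.75, 2.0 and 2.25 only, at baseline uptakes of 20% to 40%.

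The Data Analysis section plans "separate regression models that are each further stratified by potential modifiers such as gender, age, sexuality, immigration status, and other baseline characteristics", and says that modified Poisson will be used in "models for each intervention component to estimate risk ratios and 95% confidence intervals". It plans no risk difference, no table of uptake with and without a component by stratum, and no interaction on the difference scale. Nor does any other section.

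Section 9 (Limitations) adds that "a low p-value on heterogeneity tests will provide us with a signal for further investigation in a sufficiently powered future RCT". It does not say whether that test is on the ratio or the difference scale. Because the only models described estimate RRs, the ratio scale is the natural reading, but it is an inference.

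**The concern.** For an outcome such as testing at a health facility, a natural meaning of benefiting most is the number of additional people tested per 100. That number is baseline uptake × (RR − 1), so an RR gives it only together with the baseline. When two strata start from different uptake, equal RRs imply unequal gains, and the stratum with the larger RR can have the smaller gain.

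The Introduction gives a reason to expect different baselines: it describes men, immigrants, and people with low socioeconomic status or high stigma as testing less. Gender and immigration status are among the named modifiers in the Data Analysis section, and stigma is named in the sample-size section.

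At stake is the signal that the pilot passes to a later trial. Read from RRs alone, the results could point to the sub-group with the smaller absolute gain, or show no difference where the gains differ twofold. Adding an interaction term to the Poisson model would not change this, since the term would still be on the ratio scale.

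**Working it through.** **Inputs**
- Baseline uptake of 20%, 25%, 30%, 35% and 40%, and RRs of 1.75, 2.0 and 2.25: Table 1.
- Share with the component: 50% (open house) to 70% (healer test), from the sample-size section.
- Stratum size: 135 as printed in Table 1. Also 270, which is what 600 enrolled gives after excluding 10% and halving (600 × 0.90 / 2).
- Two-sided alpha of 0.05: an assumption based on the 95% CIs, since the plan states no alpha.

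**Reproducing the plan's figure.** For 135 per stratum, 30% baseline, RR 2.0 and a 50% share, Table 1 gives power 0.928. A two-proportion formula (67.5 per group, 0.30 vs 0.60) gives 0.947. Simulating a Wald test on log RR, which is closer to modified Poisson, gives 0.940. The printed value comes from 500 simulations, so these agree adequately.

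**Absolute gain** = p0 × (RR − 1)

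| Baseline p0 | RR | Uptake with component | Gain (points) |
|---|---|---|---|
| 20% | 2.0 | 40% | +20 |
| 30% | 2.0 | 60% | +30 |
| 40% | 2.0 | 80% | +40 |
| 20% | 2.25 | 45% | +25 |
| 40% | 1.75 | 70% | +30 |

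The same RR of 2.0 covers a twofold range of gain. In the last two rows, the RR and the gain rank the strata in opposite order.

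**Power to detect a difference in gain.** In each stratum, Var(RD) = p0(1 − p0)/n0 + p1(1 − p1)/n1. The SE of the contrast is the square root of the two strata's variances summed, and power is Φ(d/SE − 1.96) + Φ(−d/SE − 1.96). For 20→40% against 40→80% with 135 per stratum and a 50% share:
- Sum of p(1 − p) terms: 0.16 + 0.24 + 0.24 + 0.16 = 0.80
- SE = √(0.80/67.5) = 0.109
- d/SE = 0.20/0.109 = 1.84, so power is 0.45

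The ranges below run from a 70% to a 50% share.

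| Contrast | Difference in gain | Difference scale, n=135 | Difference scale, n=270 | Ratio scale, n=135 | Ratio scale, n=270 |
|---|---|---|---|---|---|
| 20→40% vs 40→80% (RR 2.0 in both) | 20 points | 39-45% | 66-74% | 5% | 5% |
| 25→50% vs 35→70% (RR 2.0 in both) | 10 points | 13-14% | 21-24% | 5% | 5% |
| 20→45% vs 40→70% (RR 2.25 vs 1.75) | 5 points | 7% | 9-10% | 10-12% | 15-19% |

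The 5% entries are alpha alone: with equal RRs, a ratio-scale test has nothing to find at any sample size.

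**The case against.** The strongest reply is that the contrast is stretched. Table 1's 20% to 40% is a sensitivity range around one expected value of about 30%, not a forecast of how strata differ. Everyone enrolled is a healer's patient without an HIV test result in the past year, so baselines may be closer together than in the community that the Introduction describes. This stands: the stratum baselines here are scenarios.

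Second, power. A reader might infer that moving the heterogeneity test to the difference scale would find what the RR misses. The working does not support that. Only the widest contrast has moderate power, and the 5-point reversal is close to undetectable on either scale. This also stands.

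Third, the choice of scale. The plan does not define benefiting most. Its stated purpose includes reaching people whom other testing routes miss, and for that purpose a measure that can favour low-testing strata is not plainly a defect. The RR is a valid measure, so the documents do not support making the risk difference the sole deciding scale.

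Fourth, a reader might argue that the RR's upper limit of 1/baseline hides benefit in well-testing strata. At 40% uptake the limit is 1/0.40 = 2.5, above the largest RR considered (2.25), so it does not bind within the plan's range.

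Finally, the components are self-selected and the study is not randomised, so both measures are associations. In an unadjusted model, uptake by component and stratum yields the risk difference directly, so the information exists. What is missing is a commitment to report it.

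**Conclusion.** The concern holds as a reporting gap. The plan aims to find who benefits most, and its planned output cannot show absolute gain if baselines differ. Within the plan's own range, one RR of 2.0 corresponds to gains from 20 to 40 points, and RR order and gain order can disagree (+25 against +30).

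This rests on baseline uptake differing between enrolled strata, which the Introduction makes plausible but the plan does not quantify. The masking result further assumes that the heterogeneity test is on the ratio scale.

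It would go too far to say that the pilot will choose the wrong groups for a trial. Section 9 treats a low heterogeneity p-value only as a signal and concedes limited power in small sub-groups. It would also go too far to say that a difference-scale test would reliably put the ranking right. The arithmetic is certain; how much it matters in practice depends on baselines not yet known.

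**What to change.** In the Data Analysis section, add that for each component and modifier the report will give:
- uptake with and without the component in each stratum;
- the risk difference with 95% CI, by marginal standardisation from the same modified Poisson model, beside the RR;
- heterogeneity on both the ratio and the difference scale, before any sub-group is named as benefiting most.

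State these scales in section 9 as well. Label the difference-scale contrast exploratory and associational, because the components are self-selected and power is limited.

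The cost is a sentence or two in the plan and a few lines of code, with no new data. The downside is a larger set of exploratory contrasts to interpret, and the two scales may disagree. Where they do, the report should say so rather than pick one.

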## **8. Ethical Considerations**

### Recruitment and Consent

Participants will be recruited among those who present for health care services from one of our traditional healers trained in conducting HIV counseling and testing. Participants will be recruited after their healer consultation is completed to ensure we do not impact their services. Healers will screen potential participants for eligibility (no HIV test in past year, over 18 years of age, live in Agincourt) and if they are eligible, the healers will ask if they are willing to participate in a research study. Healers will state clearly that there is no obligation to participate and that choosing not to participate will in no way impact their health care from this traditional healer. Healers will consent participants via an online consent form via tablet, so all consent forms will be online and backed up to the secure Vanderbilt REDCap cloud.

### Participant Confidentiality

The study will be conducted according to national and international standards of research ethics, to ensure that the rights of all participants will be respected. Ethical approval from the Wits Human Research Ethics Committee (Medical), the Mpumalanga Provincial Research Committee, and of the Faculty of Medicine at Vanderbilt University will be obtained before any data collection activity commences.

The involvement of individuals in the interviews will be strictly voluntary. After introducing him/herself, the interviewer will read the informed consent to the participant and answer any questions they may have. If he/she does not accept, the discussion with the interview will end. The participants will be assured of the utmost confidentiality on the part of the teams involved in the study.

Information regarding consent will not be logged anywhere and signed forms will be stored in a locked cabinet separate from transcripts and other potentially identifying information from the study. Only the principal investigators will have access signed consent forms. Transcripts will also be maintained to ensure confidentiality and access is restricted to authorized investigators. The confidentiality of the information collected will be strictly guarded.

### Adverse Events

The proposed research will establish the following data and safety monitoring procedures, in compliance with NIH requirements, to ensure participant safety and protect the validity and integrity of data. The study is low risk, with intervention content focusing on providing personal protective equipment to rural South African traditional healers. However, we acknowledge that the participant population is vulnerable and given that the focus of the research is on HIV, a stigmatized condition, the following safety plan will be implemented.

[name] will be primarily responsible for monitoring the proposed study. Together Drs. [name] and [name] (Wits), will meet regularly with the site study coordinator and research team to discuss and resolve any situations arising that relate to ethics or human subjects protection. Together with MRC/Wits Agincourt Research Unit senior field staff, they will devise and implement an appropriate remedial course of action that sufficiently addresses any critical incident or adverse event that arises. [name] will promptly inform the VU IRB, while [name] will inform the Wits HREC and Mpumalanga Province research ethics committee of any event that occurs.

Any time an adverse event occurs and at least once a year the investigators will conduct a data and safety review. During this review process, the investigators will evaluate any adverse events and determine whether the event changes the risk/benefit ratio of the study and whether modifications to the protocol or consent process are required. When necessary, they will seek recommendations from Vanderbilt University, Wits University and/or Mpumalanga Province research ethics committee.

The VU and South African (Wits and Mpumalanga Province) IRBs will also review the study proposal and annual reports will be submitted as part of the continuing review process. At this time, they will complete the following: (1) reassess the risks and benefits to participants, the informed consent process, and safeguards for human subjects; (2) review participant enrollment and retention; (3) consider any new scientific or therapeutic developments that might impact the safety of participants in the study; and (4) review any adverse events. Changes to the DSMP will be made as needed.

The investigators will adhere to the VU and South African IRBs' policies on unanticipated problems involving risks to participants or others. The following problems would require prompt reporting to the IRBs. This procedure outlines the process for reporting adverse events, serious adverse events, and unanticipated problems involving risk to participants or others.

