## **2. Objectives**

The objective of this proposal is to conduct a pilot test of a program aimed at training traditional healers to conduct HIV testing and implementing HIV testing among people living in Bushbuckridge, South Africa.

Pilot Healer-initiated HIV testing uptake and linkage to prevention services. Trust in allopathic health care and HIV stigma will be measured among participants at study enrollment and at month seven.

*Hypothesis:* HICT will increase trust in allopathic health care and reduce HIV stigma.

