#### Investigator Responsibilities

A. The Investigator submits any serious adverse event that requires reporting according to this policy and any other adverse event that may represent an unanticipated problem involving risk to participants or others as follows:

1. A "Report of Unanticipated Problem Involving Risk to Participants or Others" is submitted to the IRB as soon as possible, but no later than 7 calendar days after the Investigator first learns of the event or problem.

This form contains the Investigator's assessment of causality (related or not related to the study) and a description of the actual event;

2. The form also contains an evaluation of whether the event meets the following criteria:

- a. An event that suggests that the research places subjects or others at a greater risk of physical or psychological harm than was previously known or recognized;
- b. Unanticipated (i.e., the event was not foreseeable); and
- c. Related (i.e., likely to have been caused by the research procedures)

3. Finally, any associated materials such as medical record notations or reports with the name and medical record number of the individual redacted (removed) will be included with the report.

4. When applicable, a “Request for Amendment” indicating changes associated with the event or problem is submitted.

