#### *Serious Adverse Event (SAE) Reporting*

The Division of AIDS Table for Grading the Severity of Adult and Pediatric Adverse Events (DAIDS AE Grading Table), Version 1.0, December, 2004, will be used to determine clinical and laboratory grades of any/all grade 2 or higher events (including signs and symptoms, laboratory abnormalities, and diagnoses).

In addition, any/all deaths, disabilities, malignancies, and/or any other conditions deemed serious and/or debilitating/incapacitating by the clinical team will be reported to all involved ethical review boards. The PI will submit SAE information as required by local regulatory or other local authorities, and the research team will adhere to these stringent requirements and submit full reports detailing any SAEs in a timely fashion (i.e. in accordance with existing standards). After the end of the protocol-defined SAE reporting period stated above, the site will report serious, unexpected, clinical suspected adverse drug reactions if the study site staff becomes aware of the event on a passive basis, i.e., from publicly

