#### **D. Items from the Internalized Stigma Scale**

*If you were to test positive for HIV and told others your status...*

you would experience a break-up of your marriage or relationship.

you would experience physical abuse by your spouse/partner(s).

you would lose your job/ livelihood.

you would be treated badly at work or school.

you would lose your friends.

you would be disowned from or neglected by your family.

you would be treated badly by health professionals.

your community(village) would treat you like a social outcast.

your family would not care for you if you became sick.

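### The safety section describes a different intervention, leaves its reporting period and list of reportable problems unstated, and schedules no participant-level collection of harms from healer-delivered HIV testing

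*Combined protocol and SAP*

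**What the plan says.** Section 2 states the aim: "The objective of this proposal is to conduct a pilot test of a program aimed at training traditional healers to conduct HIV testing". Section 5 (Training Activities) covers rapid testing, pre- and post-test counselling and referral. Section 7 (Data Analysis) names three components: healer-initiated testing, additional counselling sessions and open-house attendance.

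Section 8 (Adverse Events) gives this basis for the risk level: "The study is low risk, with intervention content focusing on providing personal protective equipment to rural South African traditional healers". The next sentence qualifies it, noting that participants are vulnerable and that "given that the focus of the research is on HIV, a stigmatized condition, the following safety plan will be implemented".

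The reporting rules are then as follows.
- **Review.** The investigators hold a safety review whenever an adverse event occurs, and at least yearly.
- **Prompt reports.** A sentence just before Investigator Responsibilities announces the problems that need prompt reporting. A report is due "no later than 7 calendar days after the Investigator first learns of the event or problem".
- **Grading.** A standard severity table "will be used to determine clinical and laboratory grades of any/all grade 2 or higher events".
- **Serious events.** The ethics boards are told of "any/all deaths, disabilities, malignancies, and/or any other conditions deemed serious" by the clinical team.
- **After the period.** "After the end of the protocol-defined SAE reporting period stated above, the site will report serious, unexpected, clinical suspected adverse drug reactions", if staff become aware of them passively.

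Section 5 also provides monthly observation of healers against a procedural checklist, and says that this covers the safety of those tested.

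**The concern.** The stated reason for calling the study low risk belongs to another intervention, so ethics boards weighing risk and benefit start from a wrong description. Staff also cannot apply a reporting period that they cannot find.

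The larger issue is ascertainment. The harms to think of first when a healer gives an HIV result in the community are social and psychological: disclosure against the person's wishes, violence at home, loss of work or housing, acute distress, and a result that is wrong. If nobody asks about these, the study learns of them by chance. Section 9 presents the pilot as groundwork for a larger randomised trial. A report of few or no harms would then be hard to interpret, because it could reflect either safety or silence.

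**Working it through.** The point is textual. The plan gives no safety figure to reproduce, so the check sets the sections side by side.

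**1. Risk statement against intervention.** Section 8 names protective equipment. Sections 2, 5 and 7 describe testing, counselling, open houses and stigma training for providers. Protective equipment is an intervention component nowhere else in the document. The two descriptions do not match.

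**2. Reporting period.** The SAE Reporting text points back to a period given earlier. None is visible in Section 8 from Adverse Events to that sentence.

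**3. Drug wording.** The rule for events after the period concerns adverse drug reactions. No study drug is described.

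**4. List of reportable problems.** A list is announced, but a procedure follows. The nearest content is the set of three criteria on the report form: greater risk of physical or psychological harm than previously known, not foreseeable, and likely caused by research procedures. Which serious events must be submitted is defined by reference to the policy itself.

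**5. What each route would pick up**, taking partner violence after a result, unwanted disclosure and a wrong result as test cases:

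| Route | What it needs | What it leaves open |
|---|---|---|
| 7-day report | The investigator learns of the event | No scheduled step brings the event to the investigator |
| Unanticipated-problem criteria | The event was not foreseeable | A harm that could be foreseen does not meet this criterion |
| Serious-event clause | The clinical team judges the condition serious | Covers severe injury if known; disclosure or a wrong result need not qualify |
| Severity grading | An event of grade 2 or higher; signs, laboratory findings and diagnoses are the examples given | The documents do not show how social harms would be graded |
| Monthly observation | An observer present during the procedure | Does not see what happens at home afterwards |

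**6. Scheduled data collection.** Table 6 lists attendance, HIV status and enrolment in care at baseline and Month 6. At Month 7 it lists stigma, trust, beliefs, traditional medicine use, perceived risk and experience of the collaborative. The Appendix 2 items measure mistrust, conspiracy beliefs, perceived risk and stigma. The stigma items that touch on abuse, job loss or family rejection ask what the participant expects after disclosure, or what happens to people with HIV in general. None asks whether it happened to the participant after testing. The closest items are the Month 7 qualitative questions and the feedback on acceptability and satisfaction.

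**7. Wrong results.** The healer collects the testing outcome. The Month 6 re-test gives a partial check on negatives, but only for those who attend (the sample-size section expects about 30% uptake), and it cannot separate an earlier false negative from a new infection.

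**8. Numbers exposed.** Enrolment is 600 and assumed acceptance is 70%: 600 × 0.70 = 420 tested by a healer. For positives, the sample-size section assumes 5% to 10% of participants, so 600 × 0.05 = 30 to 600 × 0.10 = 60, but it also states 10 to 30. The conclusion does not depend on which applies.

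**The case against.** The strongest reply is that the plan has working rules. There is a 7-day clock, a criterion that covers psychological as well as physical harm to subjects or others, a clause for any serious condition, regular team meetings, a review after each event, and monthly observation that expressly includes participants' safety. Healers are trained on distress after a positive result and on recognising and referring depressive symptoms. A participant who was injured or in crisis, and whose case became known, could be reported. All of this stands. A reader might infer that no workable rule exists; the documents do not support that. The gap is in finding events.

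Three other readings are tempting and do not hold.
- A reader might infer that serious-event reporting rests on drug reactions. That wording applies only after the period ends, and the main clause has no such limit.
- A reader might infer that the whole plan rests on the protective-equipment sentence. No rule in Section 8 is tied to the risk level, and the next sentence gives vulnerability and HIV stigma as the reason for the plan.
- A reader might take Section D of Appendix 2 as the protocol's list of expected consequences. It is an anticipated-stigma scale, conditional on the participant's own disclosure. It shows that such harms could be foreseen, not that the plan predicts them.

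There is also a fair caveat about the text. The SAE section breaks off in mid-sentence and some pages were removed, so a period stated in lost text cannot be fully excluded. The consent forms and the ethics boards' own policies are not available either. The risk-statement mismatch and the absence of harm items from the schedule and surveys shown do not depend on the missing period.

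**Conclusion.** The point holds in this form. The risk statement does not describe this study, the reporting period and the list of reportable problems are not visible, the drug wording has no object, and no scheduled participant-level collection covers harms of healer-delivered testing. Followed as written, foreseeable harms can go unrecorded among roughly 420 people tested, assuming 70% acceptance of 600. How many would be missed cannot be estimated from the documents.

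The effect is on the completeness of the safety data and on what the pilot can tell a later trial. It does not touch the primary analysis or the power. A reader might also want to size it by a zero-event limit, for example 3/30 = 10% if no harm is seen in 30 positives. That limit is set by the number of people, and better capture would not change it, so it is no measure of this gap.

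The conclusion assumes that Table 6 and Appendix 2 as shown are the full schedule and survey content, and that the visible text of Section 8 is essentially continuous. The correction is worth making before enrolment.

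**What to change.** 1. Reconcile the risk statement in Section 8 with the testing and counselling intervention, and describe its risks.
2. State the event reporting period, complete the announced list of reportable problems, and reconcile the drug-reaction wording with a study that has no drug.
3. Name these as events to record, whether or not foreseeable: unwanted disclosure, partner or family violence, loss of livelihood or home, severe distress after a result, and an incorrect result.
4. Add a few items on experienced harm to the Month 7 tablet survey. A study assistant already conducts it, so the answers need not pass through the healer. Report each harm with the number of participants actually asked, since those harmed may be less likely to return.

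The cost is an ethics amendment, slightly longer survey time, and a stated referral route with a named role for participants who report harm. No new visits are needed. A single question at Month 7 will find some events late, so it supplements the existing rules and does not replace them.
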